11.2.8	Blinding Assessment.....	18
11.2.9	Adverse Event Data	18

1. Study Scope

This study is a prospective, multi-center, randomized, placebo-controlled study. A minimum of 68 subjects who suffer from acute migraine headaches and who provide written informed consent will be enrolled at a minimum of 3 clinical sites. Subjects will be randomized into one of two treatment groups (*i.e.* Avulux® device vs. control/sham device) in a one-to-one ratio. Subjects will participate in the study for a maximum of four (4) weeks after enrollment. Subjects will be directed to apply the study device specific to their study arm as soon as possible once they experience symptoms consistent with the onset of a migraine attack. Subjects will be asked to assess the severity of each headache using a pain score just prior to the application of the study device, and 2- and 4-hours following application of the device, for all severe or very severe migraine headaches that they experience while enrolled in the study.

This study will be conducted upon execution of a clinical study agreement and receipt of Institutional Review Board or Ethics Committee (IRB/EC) approval from each participating site.

2. Principle of the Device

Avulux® is intended to reduce the severity of headache pain in adult patients diagnosed with episodic migraine headache. In this study, the investigative Avulux® device shall consist of a pair of optical filters in the form of spectacle lenses, provided in a standard spectacle frame; the lenses contain a dye that effectively blocks light at specified wavelength ranges while minimizing distortion of the visible spectrum. The optical filters block a portion of the optical spectrum that is suspected to stimulate photophobic responses that trigger some, and exacerbate most, migraines.

The control/sham device for this study shall be a pair of plastic lenses provided in a standard spectacle frame, which will have negligible light-blocking properties at the optical wavelengths which are blocked by the Avulux® device.

3. Study Objectives

3.1 Primary Objective

The primary objective of this study is to evaluate the efficacy of the Avulux® device in reducing the impact of migraine headaches, as measured by improvement in an 11-point pain scale after 2 hours of device application, when compared to a control/sham device.

3.2 Secondary Objective

The secondary objective of this study is to evaluate the efficacy of the Avulux® device in reducing the impact of migraine headaches, as measured by improvement in an 11-point pain scale after 4 hours of device application, when compared to a control/sham device.

3.3 Exploratory Objectives

Exploratory objectives for this study are:

- To compare the proportion of subjects who show quantifiable improvement in overall migraine impact (as measured by a change in migraine pain from severe to mild/no pain) when using the Avulux® device vs. a control/sham device;
- To compare the proportion of subjects who require adjunctive medication to control their migraine headache when using the Avulux® device vs. a control/sham device; and
- To compare the proportion of subjects suffering from light sensitivity as a result of their migraine headache when using the Avulux® device vs. a control/sham device.

4. Study Endpoints

4.1 Primary Endpoint

The primary endpoint variable is the change in migraine pain as measured on an eleven-point pain scale, defined as the pain score after an elapsed time of 2 hours following application of the device minus the pain score at onset of migraine symptoms, with respect to the first severe or very severe migraine headache (defined as a pain score of 6 or greater at onset of migraine symptoms) experienced by an enrolled subject.

4.2 Secondary Endpoint

The secondary endpoint variable is the change in migraine pain as measured on an eleven-point pain scale, defined as the pain score after an elapsed time of 4 hours following application of the device minus the pain score at onset of migraine symptoms, with respect to the first severe or very severe migraine headache (defined as a pain score of 6 or greater at onset of migraine symptoms) experienced by an enrolled subject.

4.3 Exploratory Endpoints

Exploratory endpoint variables are:

- The proportion of subjects who report mild or no symptoms (defined as a pain score of 3 or less) after an elapsed time of 2 hours following application of the device, with respect to their first severe or very severe migraine headache;
- The proportion of subjects who require abortive medication to control their first severe or very severe migraine headache within 8 hours following application of the device; and
- The proportion of subjects who report sensitivity to light after elapsed times of 2 hours and 4 hours following application of the device, with respect to their first severe or very severe migraine headache.

5. Inclusion/Exclusion Criteria

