6.4 Procedures and Assessments

Subjects will be directed to:

- apply the study glasses at the first onset of aura, or as soon as possible once they experience symptoms consistent with the onset of a migraine attack.
- avoid taking abortive medication for the first four hours of a migraine attack. If abortive medications cannot be avoided, the subject should document use.
- record the following information for the first (and all subsequent) severe or very severe migraine headaches that they experience while enrolled in the study:
 - The date and time of symptom onset;

¹ Kwong WJ and Pathak DS. Validation of the eleven-point pain scale in the measurement of migraine headache pain. *Cephalgia* 2007; 27: 336-342.

- The pain score (as assessed on the 11-point pain scale) just prior to the application of the study glasses (score needs to be greater than or equal to 6 to qualify as a severe or very severe headache);
- The time at which the study glasses are applied;
- Whether the subject was wearing prescription eyewear in addition to the study glasses, or whether the study glasses alone were worn;
- The pain score (as assessed on the eleven-point pain scale) 2 hours after the study glasses are applied;
- The pain score (as assessed on the eleven-point pain scale) 4 hours after the study glasses are applied;
- The type of abortive medication taken (if any) to control headache symptoms, the dosage taken, and the time at which the medication is taken; and
- Any experience of light sensitivity within 4 hours after the study glasses are applied, and the time at which light sensitivity is first experienced.

Subjects will participate in the study for a maximum of four (4) weeks \pm 3 days after enrollment; if a given subject does not experience a severe or very severe migraine headache within four (4) weeks, that subject will not be included in the evaluable study population.

Study coordinators will contact subjects once per week to ensure they are wearing the study device as instructed, and that they are recording the requested information related to their headaches. These weekly contacts will also enable coordinators to identify and address any barriers to adherence with the protocol.

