11.2.1 Analysis Populations

The *intention-to-treat* (ITT) population shall be defined as the population of all enrolled subjects who were assigned to a study group and who experienced a minimum of one severe or very severe headache within 4 weeks of enrollment. This population shall include subjects who were non-compliant with study procedures, and subjects who were assigned to the incorrect device specific to their study group.

The *per-protocol* population shall be defined as the population of all enrolled subjects who were assigned to the correct device specific to their study group, who experienced a minimum of one severe or very severe headache within 4 weeks of enrollment, and who were compliant with study procedures throughout the duration of their enrollment in the study.

Analyses of the primary and secondary endpoints shall be conducted using data from intention-to-treat population. Analyses of exploratory endpoints shall be conducted using data from the per-protocol population.

² Olsen MF, Bjerre E, Hansen MD *et al.* Pain relief that matters to patients: systematic review of empirical studies assessing the minimum clinically important difference in acute pain. *BMC Medicine* 2017, 15: 35.

³ Farrar JT, Young JP Jr., LaMoreaux L *et al.* Clinical importance of changes in chronic pain intensity measured on an 11-point numerical pain rating scale. *Pain* 2001, 94: 149-158.

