11.2.7 Analysis of Exploratory Endpoints

In order to compare the proportion of subjects who report mild or no symptoms after an elapsed time of 2 hours using the active device to the corresponding proportion using the control/sham device, subjects will be stratified into two categories within each study arm, using the baseline pain score (6-7 vs. 8-10) as the basis for stratification. Within each of the two strata, the number of subjects with a pain score of ≤ 3 after 2 hours and the number of subjects with a pain score of > 3 after 2 hours shall be tabulated for both the active device and for the

control/sham device; results for each stratum shall be displayed in a 2 x 2 table. A Cochran-Mantel-Haenszel test shall be conducted to test the hypothesis of lack of association between the proportion of subjects reporting mild or no symptoms after 2 hours and the type of device, across all strata. An estimate of the pooled odds ratio and the associated exact 95% confidence interval will be computed, along with the p -value associated with the test of the null hypothesis.

The procedures described above shall also be conducted in order to compare the proportion of subjects who require abortive medication to control their migraine headache within 8 hours between the two device types, and to compare the proportion of subjects who report sensitivity to light after elapsed times of 2 hours and 4 hours between the two device types.

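### The exploratory 2-hour responder endpoint has no rule for abortive medication taken before the 2-hour score, so drug relief can count as response or remove the subject from the analysis

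*Combined protocol and SAP*

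**What the plan says.** Section 3.3 sets the aim: "To compare the proportion of subjects who show quantifiable improvement in overall migraine impact", active device against sham. Section 4.3 turns this into "The proportion of subjects who report mild or no symptoms (defined as a pain score of 3 or less) after an elapsed time", here 2 hours, for the first severe or very severe headache. Section 11.2.7 tabulates subjects as at or below 3 against above 3 and uses a Cochran-Mantel-Haenszel test "to test the hypothesis of lack of association between the proportion of subjects reporting mild or no symptoms after 2 hours and the type of" glasses worn. The only stratifier is baseline pain, 6-7 against 8-10.

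On medication, section 6.4 directs subjects to "avoid taking abortive medication for the first four hours of a migraine attack" and then adds: "If abortive medications cannot be avoided, the subject should document use". The diary captures the type of drug, "the dosage taken, and the time at which the medication is taken".

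On population, section 11.2.1 states: "Analyses of exploratory endpoints shall be conducted using data from the per-protocol population". That population is limited to subjects with the correct device and a qualifying headache "who were compliant with study procedures throughout the duration of their enrollment in the study". Nothing says whether documented early use breaks compliance.

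Section 11.2.5 compares early rescue use between arms by Fisher's exact test and moves to ANCOVA if the arms differ. Section 11.2.6 carries this to the 4-hour endpoint. Section 11.2.7 contains no such step.

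**The concern.** The plan accepts that early rescue can distort the 2-hour pain score, because 11.2.5 tests for it on the primary endpoint. The responder endpoint is the same score from the same headache, cut at 3, and has no protection.

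A subject who medicates before the 2-hour score can be handled in two ways under the current text. If kept, the subject is a responder whenever the drug brings pain to 3 or less, and that relief is credited to the assigned glasses. If removed as non-compliant, the subject leaves the analysis because of something that happened after randomisation and may depend on the device. Under both readings the comparison can shift when rescue differs by arm, and the choice between them could be made after the data are seen.

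**Working it through.** **Plan's own figures.** The documents give no figure for the responder endpoint. The primary sample size in 11.1 reproduces: for a difference of 2, SD 2.0 and two-sided 0.05, the t-test has power 0.950 at 27 per arm, and 27/0.80 = 33.75, rounded up to 34. Nothing stated in the plan depends on the responder definition, so no stated number is wrong.

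**The text, followed for one subject.** The subject medicates at 30 minutes and scores 3 at 2 hours. By 4.3 and 11.2.7 this is a response. By 11.2.3 only missing exploratory values are dropped, and this value is not missing. By 11.2.1 the subject is in or out according to an undefined compliance rule. The check in 11.2.5 does not apply.

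**Illustration of size.** From 11.1: mean improvement 4 (active) and 2 (sham), SD 2.0. Assumed here: baseline 7, normal changes, cut at 3.5, only subjects who would not respond on the device alone take early medication, and 30% to 50% of those reach 3 or less on the drug.

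Device-only response:
- Active: Φ((3.5 − 3)/2) = Φ(0.25) = 59.9%
- Sham: Φ((3.5 − 5)/2) = Φ(−0.75) = 22.7%
- Difference 37.2 points, odds ratio 5.1

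Let p be device-only response, r the share of would-be non-responders who rescue before 2 hours, and s the share of those relieved.
- Counted as written: p + (1 − p)·r·s
- Rescuers excluded: p / [p + (1 − p)(1 − r)]
- Rescuers counted as non-responders: p

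Sham rescues more (r = 10% active, 30% sham):
- As written, active: 0.599 + 0.401 × 0.10 × (0.3 to 0.5) = 61.1% to 61.9%
- As written, sham: 0.227 + 0.773 × 0.30 × (0.3 to 0.5) = 29.6% to 34.3%
- Difference 31.5 to 27.6 points, odds ratio 3.7 to 3.1
- Excluded: 62.4% against 29.5%, difference 32.9 points

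Active rescues more (r = 30% active, 10% sham):
- As written: 63.5% to 65.9% against 25.0% to 26.5%, difference 38.5 to 39.4 points
- Excluded: 68.1% against 24.6%, difference 43.5 points

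No device effect (22.7% in both arms, r = 10% and 30%):
- As written: 25.0% to 26.5% against 29.6% to 34.3%, a spurious 4.6 to 7.7 points in favour of the arm that rescues more
- Excluded: 24.6% against 29.5%, a spurious 4.9 points in the same direction

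**Range over assumed baselines 6 to 8.** Device-only differences are 37.2, 37.2 and 29.6 points at baselines 6, 7 and 8. As written, more rescue in sham removes 4.7 to 10.4 points, and more rescue in active adds 0.2 to 4.5 points.

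**The proposed rule under a less favourable assumption.** Suppose there is no device effect, and 10% of active and 30% of sham subjects medicate early whether or not they would have responded. Counting them as non-responders gives 0.227 × 0.9 = 20.4% against 0.227 × 0.7 = 15.9%, a spurious 4.5 points in favour of the device.

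**The case against.** A reader might infer that the plan definitely counts drug-relieved subjects as device successes. The documents do not go that far. Section 6.4 first tells subjects to avoid abortive medication for four hours, and 11.2.1 requires compliance, so these subjects could be excluded. The wording on documented use in 6.4 leans towards keeping them. So does the separate endpoint in 4.3 on abortive use within 8 hours: it uses the same per-protocol population and would lose its earliest users if such use were non-compliance. Neither settles the matter, and exclusion would not cure the distortion.

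A reader might also infer that the endpoint is biased towards the device, or that it cannot answer its objective. Direction depends on which arm rescues more, and more rescue in sham works against the device. Counting response regardless of medication is a recognised treatment-policy comparison. It is not stated as the intention, however, and it sits poorly with 11.2.5, which treats early rescue as a possible effect to be controlled on the same score.

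Two further points have weight. Section 11.2 defers detail to a SAP due before database lock, so the rule can still be set there; that is a reason to write it now. Imbalance would also be visible, since 11.2.5 compares early rescue by arm and abortive use within 8 hours is its own endpoint. Visibility does not correct the responder comparison. Extending the Fisher test would not be enough either: at 27 per arm its power to detect 10% against 30% is about 31%.

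The objection that stands in full is that counting medicated subjects as failures is not neutral. If subjects who guess they have sham medicate sooner, that rule can favour the device.

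**Conclusion.** The point holds as a gap in the endpoint definition and in the compliance rule. Response is defined by the 2-hour score alone, early medication is foreseen, and no passage says how it is handled for this endpoint. More rescue in sham dilutes the device effect; more in active inflates it. At baseline 7 with the assumed rescue shares, counting as written removes about 6 to 10 points or adds about 1 to 2 points, and excluding rescuers removes about 4 points or adds about 6. These sizes rest on assumed baseline, rescue and drug-relief rates and on the assumption that only would-be non-responders medicate early. They show that the handling matters, and they do not predict the trial's result. Severity is low: the endpoint is exploratory, has no sample-size claim attached, and does not affect the primary analysis.

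**What to change.** In 4.3 and 11.2.7, define a responder as a subject with a score of 3 or less at 2 hours and no abortive medication between symptom onset and that score. Count subjects who medicated in that interval as non-responders. Tie the interval to the 2-hour score itself, because the score is timed from putting on the glasses while the window in 11.2.5 runs from symptom onset.

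In 11.2.1, state that documented abortive use does not by itself remove a subject from the population for this endpoint.

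Report the as-written definition as a sensitivity analysis. Beside both results, show rescue before the 2-hour score by arm and the blinding assessment from 11.2.8.

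The cost is a sentence in each of the three sections and no new data, since medication times are already in the diary. The downside is that responder rates fall, possibly noticeably in the arm that rescues more: in the illustration with more sham rescue, sham drops from 29.6%-34.3% to 22.7% and active from 61.1%-61.9% to 59.9%. If guessing the assignment drives early medication, the new rule could favour the device, which is why the results should be shown together. The change concerns the analysis only and leaves what subjects may take untouched.

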11.2.3 Handling of Missing Data

In the intention-to-treat population, any missing pain scores at time points of 2 and 4 hours after application of the device shall be imputed using a multiple imputation procedure, with study arm, age, sex, baseline pain score, number of severe or very severe headaches experienced while enrolled in the study, and pain scores at 2 and 4 hours after application of the device for subsequent severe or very severe headaches experienced while enrolled in the study as predictors. Imputation procedures shall utilize predictive mean matching.⁴ A total of 50 sets of multiple imputations shall be generated; the analysis of the primary endpoint shall be conducted for each set, and a pooled estimate of the difference in mean improvement between the two devices will be computed, along with a 95% interval estimate and p -value associated with the null hypothesis.

In the per-protocol population, subjects with a missing value of an exploratory endpoint will not be included in the evaluable population for that endpoint.

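### The 8-hour abortive-medication endpoint has no scheduled entry after 4 hours and no rule for a blank, so unrecorded late use cannot be told apart from no use

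*Combined protocol and SAP*

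**What the plan says.** - **Endpoint.** Section 4.3 counts subjects who "require abortive medication to control their first severe or very severe migraine headache within 8 hours following application of the device". Section 11.2.7 keeps that window and applies the stratified Cochran-Mantel-Haenszel procedure to "compare the proportion of subjects who require abortive medication to control their migraine headache within 8 hours between the two device types".
- **Scheduled entries.** Section 6.4 asks for pain scores just before application, at 2 hours, and finally "The pain score (as assessed on the eleven-point pain scale) 4 hours after the study glasses are applied". It mentions no 8-hour entry.
- **Medication item.** Section 6.4 asks for "The type of abortive medication taken (if any) to control headache symptoms, the dosage taken, and the time at which the medication is taken". It sets no time limit. The light-sensitivity item in the same list does have one: "Any experience of light sensitivity within 4 hours after the study glasses are applied".
- **Instruction on use.** Subjects are told to "avoid taking abortive medication for the first four hours of a migraine attack. If abortive medications cannot be avoided, the subject should document use".
- **Missing data.** Exploratory endpoints are analysed in the per-protocol population (Section 11.2.1). There, Section 11.2.3 says that "subjects with a missing value of an exploratory endpoint will not be included in the evaluable population for that endpoint". Neither section says whether an empty medication entry is a missing value or a non-user.

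**The concern.** The endpoint window is twice as long as the schedule of entries that serves it. The avoidance instruction also tends to move medication use later, towards the part of the window with no scheduled entry. (Avoidance is counted from the start of the attack and the endpoint from application, so the overlap is approximate.)

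Because medication is entered only if taken, a correctly completed record for a non-user is empty. So is the record of someone who took a tablet at hour 6 and never reopened the diary. The analyst needs to separate these two subjects, and the data as specified give no means of doing so.

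This endpoint carries one of the three exploratory objectives in Section 3.3, the need for adjunctive medication. If completeness of late recording differed between arms, the difference could look like a medication saving, or could hide one. The information cannot be recovered once the data are collected.

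**Working it through.** **1. The plan's own figure.** The documents give no expected rate, effect or sample size for this endpoint. The only sizing, in Section 11.1, is for the 2-hour pain change: difference 2, SD 2.0, two-sided alpha 0.05. It reproduces: noncentral-t power at 27 per arm is 0.950, and 27 / (1 − 0.20) = 33.75, rounded up to 34 per arm. It has no bearing on the medication endpoint. It is used here only to supply n = 27 per arm for illustration.

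**2. What each record would show at analysis.**

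| Subject | Medication entry | Can be classified? |
|---|---|---|
| Took medication, recorded it with its time | Filled | Yes; application time is also recorded, so the 8-hour window can be derived |
| Took none | Blank | No |
| Took some at 4–8 hours, did not record it | Blank | No |

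The last two rows are identical. Excluding missing values requires knowing which blanks are missing, and the listed items do not show this. Restricting to compliant subjects does not help either, unless the non-recording is visible, and here it looks like compliance.

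**3. What could follow if blanks were coded as no use.** All rates below are assumptions. Let a be the proportion first using medication by 4 hours (taken as fully recorded), b the proportion first using it at 4–8 hours, and m the share of b left unrecorded. The observed rate is a + b(1 − m). Power is from the two-proportion normal approximation with pooled variance under the null, two-sided 0.05, 27 per arm.

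*Equal under-recording in both arms:*

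| Scenario | m | Active | Sham | Difference | Odds ratio | Power |
|---|---|---|---|---|---|---|
| A: active 20% + 10%, sham 30% + 20% | 0 | 30% | 50% | 20 points | 0.43 | 32% |
| | 0.5 | 25% | 40% | 15 points | 0.50 | 21% |
| | 1 | 20% | 30% | 10 points | 0.58 | 13% |
| B: active 10% + 30%, sham 40% + 20% | 0 | 40% | 60% | 20 points | 0.44 | 31% |
| | 0.5 | 25% | 50% | 25 points | 0.33 | 47% |
| | 1 | 10% | 40% | 30 points | 0.17 | 73% |

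In A the contrast shrinks; in B it grows.

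*Proportional late use.* Take true 8-hour use of 35% and 60%, with 80% of it after hour 4 and m = 0.3 in both arms. The retained fraction is 0.2 + 0.8 × 0.7 = 0.76. Observed rates are 0.35 × 0.76 = 26.6% and 0.60 × 0.76 = 45.6%. The difference falls from 25 to 19 points and power from about 45% to 30%.

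*Unequal under-recording.* Take true use of 50% in both arms, 80% of it late, with 20% of late use unrecorded in the active arm only. Observed active use is 0.50 × (0.2 + 0.8 × 0.8) = 42%, against 50% for sham: an 8-point difference where none exists. The standard error of a difference near 50% at 27 per arm is √(2 × 0.25 / 27) = 13.6 points, so a shift of this size would lie within sampling noise.

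**The case against.** The strongest reply is that late use falls within what subjects are asked to record. The medication item has no time limit and asks when the medication was taken, while the neighbouring light-sensitivity item is expressly limited to 4 hours. Recording a tablet when it is taken is a legitimate method and needs no timed prompt. This stands: use at 4–8 hours is recordable. What is missing is a positive confirmation of non-use.

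A reader might infer that the plan counts unrecorded late use as no use. No section says so. The only stated rule excludes missing values; the gap is that a blank is not assigned to either category. A reader might also infer that medication use is understated in both arms, or that the active device is favoured. The first depends on the unstated coding and on under-recording that is not documented. The second depends on rates the documents do not give, and scenarios A and B show that the contrast can move either way.

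Three safeguards deserve credit, though none closes the gap.

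- Weekly contacts check that subjects are recording what is asked. They may come days after the attack, though, and a blank in an if-taken item looks complete.
- The diary form is not in the documents and may contain a yes/no box. The protocol's list of items does not require one.
- Section 11.2 promises a detailed analysis plan before database lock. That plan could define how blanks are coded, but it could not recover what was never recorded.

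**Conclusion.** The point holds in a limited form. The 8-hour window extends beyond the last scheduled entry, non-use is never explicitly confirmed in the items Section 6.4 lists, and the coding of a blank is undefined. Unrecorded use at 4–8 hours may therefore be read as no use, and the exclusion rule in Section 11.2.3 cannot be applied reliably.

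No bias can be sized or signed from the documents. The figures above show what could happen under assumed rates, assumed under-recording and a coding rule the plan does not state; they are not estimates for this trial. The power losses concern an endpoint the trial was not sized for.

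Severity is minor: one exploratory endpoint in the per-protocol population. The primary and secondary pain endpoints are unaffected, and the early-rescue comparison in Section 11.2.5 concerns the first 2 hours after symptom onset, which is not the part of the window in question. It is still worth correcting before data collection, because the change is cheap and cannot be made afterwards.

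**What to change.** - **Section 6.4:** add one diary entry at 8 hours after application: *Any abortive medication since applying the glasses? Yes / No; if yes, type, dosage and time.*
- **Section 6.4, weekly contact:** have coordinators query any 8-hour entry left blank.
- **Section 11.2.7:** state that a subject is a user if any use within the 8 hours is recorded, a non-user only with an explicit No covering the 8 hours, and otherwise missing under Section 11.2.3.

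This changes only recording and coding; the instructions on taking medication stay as they are. The cost is one more entry per attack, a short addition to the weekly call, and a few explicit missing values that would otherwise be hidden among the blanks.

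### The light-sensitivity endpoint needs status at 2 and at 4 hours, but section 6.4 collects only any occurrence within 4 hours and the time of the first, so the endpoint cannot be computed as defined

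*Combined protocol and SAP*

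**What the plan says.** - **Objective (section 3.3).** "To compare the proportion of subjects suffering from light sensitivity as a result of their migraine headache", by device. No time point is set.
- **Endpoint (section 4.3).** "The proportion of subjects who report sensitivity to light after elapsed times of 2 hours and 4 hours following application of the device". Only each subject's first qualifying headache counts.
- **Analysis (section 11.2.7).** The stratified Cochran-Mantel-Haenszel procedure is repeated "to compare the proportion of subjects who report sensitivity to light after elapsed times of 2 hours and 4 hours". Under section 11.2.1, "Analyses of exploratory endpoints shall be conducted using data from the per-protocol population".
- **Data collected (section 6.4).** For light sensitivity: "Any experience of light sensitivity within 4 hours after the study glasses are applied, and the time at which light sensitivity is first experienced". For pain: "The pain score (as assessed on the eleven-point pain scale) 2 hours after the study glasses are applied", with a matching item at 4 hours and a score just before application.

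Nothing else in the documents collects light sensitivity. The closing questionnaire at the end of section 6.4 covers wearability, ease of use and the subject's guess at the device.

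**The concern.** The endpoint is worded for two time points, while the data item is worded for one 4-hour window. Pain is scored at exactly the times its endpoints need; light sensitivity is not. What can be derived is a cumulative measure: whether light sensitivity had occurred at all by 2 hours, and by 4 hours. That measure can only stay level or rise between the two times. It also codes a subject whose photophobia cleared after the glasses went on the same as one whose photophobia persisted.

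Section 2 describes the device as filtering light suspected of provoking photophobic responses, so this outcome lies close to the stated mechanism. Headaches count only if pain is already 6 or more just before application, so light sensitivity may well be present by then. Benefit would then appear largely as resolution, which a first-occurrence item misses unless it is immediate.

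**Working it through.** The plan states no rate, effect or power for this endpoint, so there is no figure to reproduce. The check is one of wording and logic, followed by two illustrations on assumed numbers.

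**1. What the endpoint wording means.** The same expression for elapsed time defines the primary endpoint (4.1), the secondary endpoint (4.2) and the first exploratory endpoint, "mild or no symptoms (defined as a pain score of 3 or less) after an elapsed time of 2 hours". All three are values at a time point. Where section 4.3 intends a window, for abortive medication, it uses *within* 8 hours. The light-sensitivity endpoint follows directly and uses the time-point wording. The data item in 6.4 uses *within*.

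**2. What the record determines.** All on/off courses of light sensitivity on an hourly grid from 0 to 4 hours were enumerated, and each was mapped to the record (any occurrence, time of first) and to the endpoint (status at 2 h, status at 4 h).

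| Record | Status at 2 h | Status at 4 h |
|---|---|---|
| No occurrence | absent | absent |
| First occurrence between 2 h and 4 h | absent | either |
| First occurrence before 2 h | either | either |

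For onset before 2 hours all four combinations are possible. Presence at 2 h or 4 h is certain only if onset falls exactly at that time.

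**3. How wide the bounds are (assumed counts in an arm of 27).** The upper bound at 2 h is (onset before 2 h)/27. At 4 h it is (onset before 2 h + onset from 2 to 4 h)/27. The lower bound is 0 in each case.

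| Onset before 2 h / 2 to 4 h / none | 2 h proportion | 4 h proportion |
|---|---|---|
| 12 / 4 / 11 | 0 to 12/27 = 44% | 0 to 16/27 = 59% |
| 18 / 3 / 6 | 0 to 18/27 = 67% | 0 to 21/27 = 78% |
| 22 / 2 / 3 | 0 to 22/27 = 81% | 0 to 24/27 = 89% |

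The missing-data rule in 11.2.3, which leaves out subjects with a missing exploratory value, does not help. In the 18/3/6 example it would keep 3 + 6 = 9 subjects at 2 h and 6 at 4 h, all of them negative.

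**4. What is lost if the cumulative measure is used instead (all rates assumed).** Let p be the proportion light sensitive around application. Resolution by 2 h is 0.50 (active) and 0.20 (sham), with no new onset. Let f be the share of resolution that is immediate, so that the subject can correctly answer no for the period after application; f is first taken as equal in both arms.

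- True difference at 2 h = p × (0.50 − 0.20) = 0.30p
- Recorded proportion = p × (1 − f × resolution)
- Recorded difference = 0.30pf

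| p | True difference (points) | f = 0 | f = 0.25 | f = 0.50 | f = 1 |
|---|---|---|---|---|---|
| 0.60 | 48 − 30 = 18 | 0 | 4.5 | 9 | 18 |
| 0.80 | 64 − 40 = 24 | 0 | 6 | 12 | 24 |
| 0.95 | 76 − 47.5 = 28.5 | 0 | 7.1 | 14.3 | 28.5 |

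If f differs by arm, the recorded difference is p × (0.50 f_active − 0.20 f_sham). At p = 0.60 it runs from 0.60 × (−0.20) = −12 points (f_active = 0, f_sham = 1) to 0.60 × 0.50 = +30 points (f_active = 1, f_sham = 0), against a true 18. The error need not be a simple dilution.

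**The case against.** The best counter-argument is that the endpoint was meant cumulatively. Section 6.4 asks for the time of first light sensitivity, no other section uses that time, and its natural use is to split first occurrence at 2 and 4 hours. The objective in 3.3 sets no time point. On that reading the Cochran-Mantel-Haenszel test can be run. The reading is possible, but the protocol's own usage favours the other one. If the cumulative measure was intended, 4.3 and 11.2.7 still need to say so.

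Second, the case report forms are not among the documents and may ask for more. That stands as a limit on what can be known, but section 6.4 as written does not require it. The separate analysis plan promised in 11.2 could define a derivation; it could not supply status that nobody recorded during the attack.

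Third, the percentages in the illustration are assumed, and equal f in both arms is doubtful when only one device blocks the relevant wavelengths. Both criticisms are fair. The figures show scale only, and the logical point does not need them.

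Finally, the endpoint is exploratory, some subjects' status is known, and the proportions can be bounded. All true, and this limits the priority. The bounds are nevertheless too wide to support the planned comparison.

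**Conclusion.** The concern holds. Followed exactly, the plan leaves one stated endpoint and its test not computable, because status at 2 and 4 hours is undetermined for subjects with earlier onset. This rests on reading the endpoint as status at a time point, which is how the protocol uses the same wording for pain, and on section 6.4 being the full data requirement.

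The size cannot be taken from the documents. Under the assumed rates with equal f, a true 2-hour difference of 18 to 28.5 points is recorded as anything from 0 to its full size.

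The objective in 3.3 can still be partly addressed, since the proportion with any light sensitivity is available in each arm and prevention or immediate suppression could be seen. The effect is confined to one of three exploratory endpoints in the per-protocol population. The change should be made, but it does not bear on the trial's main conclusion.

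**What to change.** **Preferred.** In section 6.4, add a yes/no entry for whether light sensitivity is present now, at the three existing pain-score times: just before application, 2 hours and 4 hours. In 4.3 and 11.2.7, state that the endpoint is presence at 2 hours and presence at 4 hours. The 2- and 4-hour entries are what the endpoint needs; the pre-application entry allows a supportive analysis that takes account of initial status. Keep the stratification by baseline pain.

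*Cost:* three yes/no entries per headache, made when the subject is already recording pain, and an amendment to 4.3, 6.4 and 11.2.7 under section 10.2. It has to be in place before the headaches are recorded.

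**Fallback if data collection cannot change.** Redefine the endpoint in 4.3 and 11.2.7 as first occurrence by 2 hours and by 4 hours, and state that resolution cannot be assessed.

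*Cost:* text changes in two sections, and the loss of any assessment of relief from light sensitivity already present.
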